5.1. Sample Size

Approximately 60 subjects (20 per cohort) are planned to be randomized, 15 receiving VAL-181388 and 5 receiving placebo within each cohort. Formal sample size calculations were not performed as this is a descriptive safety and immunogenicity study with no formal null hypotheses being tested.

5.2. Randomization and Blinding

Within each dose level cohort, 20 subjects will be randomly assigned to receive either VAL-181388 (25, 50, or 100 µg) or placebo in an overall ratio of 3:1. The first 4 subjects within each dose level cohort will be randomly assigned to receive VAL-181388 (25, 50, or 100 µg) or placebo in a 3:1 ratio. Only after review by the internal safety team (IST) of the blinded safety data (reactogenicity, safety laboratory results, and AEs) through 7 days following the first vaccination of the sentinel safety lead-in for each cohort planned, will approval be given to allow randomization of the remainder of that cohort. The remaining 16 subjects within each dose level cohort will be randomly assigned to receive either VAL-181388 (25, 50, or 100 µg) or placebo in a 3:1 ratio.

This is an observer-blinded study. The investigator, study subjects, site monitors, and study site personnel will be blinded to the study drug administered, with the following exceptions:

- Unblinded pharmacy personnel (of limited number) will be assigned to perform drug accountability procedures and to prepare and administer VAL-181388 (or placebo) to all subjects. The unblinded pharmacy personnel will have no other study functions other than study drug management, documentation, accountability, preparation, and administration. They will not be involved in subject evaluations and will not reveal the study drug identity to either the subject or study site personnel involved in the conduct of the study, except in the case of an emergency.
- An unblinded study monitor, not involved in other aspects of monitoring, will be assigned as the drug accountability monitor. They will have responsibilities to ensure the site is following all proper drug accountability, preparation, and administration procedures.

- An unblinded statistician will provide a descriptive analysis of safety and immunological endpoints after the completion of each dosing cohort. The interim analyses of immunogenicity data will be performed as outlined in Section 11.

The treatment assignment will be concealed by having the unblinded pharmacy personnel prepare the study drug in a secure location that is not accessible to other study personnel. The syringe used will maintain the blind at the time of vaccination (eg, a sleeve will be used should the vaccine substance be distinguishable in appearance between the VAL-181388 and placebo). The unblinded pharmacy personnel will conduct the vaccination procedure. Once the vaccination is completed, the blinded study staff will take over further assessments and interactions with the subjects. Access to the randomization code will be strictly controlled at the pharmacy.

5.2.1. Breaking the Blind

A subject or subjects may be unblinded in the event of an SAE or other event, or if there is a medical emergency requiring the identity of the drug to be known to properly treat a subject. If a subject becomes seriously ill or pregnant during the study, the blind will be broken only if knowledge of the administered study drug will affect that subject's treatment options. In the event of a medical emergency requiring identification of the study drug administered to an individual subject, the investigator will make every attempt to contact the medical monitor to explain the need for opening the code within 24 hours of opening the code. The investigator will be responsible for documenting the time, date, reason for the code break, and the names of the personnel involved.

5.3. Analysis Sets

The following analysis sets will be used: All Enrolled Subjects set, Randomized set, Safety set, Per-Protocol (PP) sets and Intent-to-Treat (ITT) sets.

5.3.1. All Enrolled Subjects Set

The All Enrolled Subjects set will include subjects who signed the ICF. The All Enrolled Subjects set will only be used for descriptive purposes.

5.3.2. Randomized Set

The Randomized set will include all subjects who were randomly assigned to the study including sentinel safety subjects. This set will only be used for descriptive purposes.

5.3.3. Safety Set

The Safety set will include all subjects who received at least 1 dose of study drug (VAL-181388 or placebo). All subjects in the Safety set will be analyzed according to the study drug actually received and not according to the study drug the subject was randomly assigned to receive, in the event there is a discrepancy.

5.3.4. Per-Protocol Sets

The PP sets will be defined separately for Part A and the entire study to support the primary assessments of immunogenicity in Part A and immune persistence in Part B.

The Primary PP set will include all subjects in the Randomized set who, in Part A (Visit 1 through Visit 7), did not observe any major protocol violation, received vaccination within the acceptable vaccination window (their full dose(s) of assigned study drug), had blood collection within accepted visit windows, and had both a pre-vaccination blood sample and at least 1 blood sample at Visit 4 or Visit 7 available for immunogenicity testing.

The Persistence PP set will include all subjects in the Primary PP set who, in Part B (Visit 8 through Visit 19), did not observe a major protocol violation, had blood collection within accepted visit windows, and had at least 1 blood sample at Visit 12 or Visit 19 available for immunogenicity testing.

All subjects in the PP sets will be analyzed according to the study drug the subject was randomly assigned to receive and not according to what was actually received, in the event there is a discrepancy. In the case where there is not a paired sample for the specific time point that data will not be included in the analysis. The process for determining major protocol violations will be provided as a separate study document.

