### **3.4.6        Treatment Compliance**

All doses of study drug will be administered at the study site under direct observation of study site personnel and appropriately recorded (date and time) in the eCRF. Site personnel will confirm that the subject has received the entire dose of study drug. If a subject does not receive study drug or does not receive all of the planned doses, the reason for the missed dose will be recorded in the source documents.

Subjects that miss the second vaccination due to noncompliance with the visit schedule and not due to a cohort pause will still be required to follow the original visit and testing schedule. Specifically, these subjects will be asked to undergo blood collection to comply with a second immune test at 56 (+10) days (Visit 7) following the first vaccination.

The study site is responsible for ensuring subjects comply with the study windows allowed. Should a subject miss a visit, every effort will be made to contact the subject and achieve a visit within the defined visit window. If a subject exceeds their post-vaccination visit in excess of 28 days from the scheduled visit or misses a vaccination schedule by more than 28 days (eg, 28 days beyond the scheduled time of vaccination) then that visit will be classified as a missed

visit and the subject will continue with subsequent visits for Parts A and B of the study. All safety requirements of the missed visit will be captured and included in the follow-up visit (eg, safety laboratory testing, memory aid review for reactogenicity, as applicable).

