The immunogenicity analyses will be performed separately for the PP sets and the ITT sets. Part A (Visit 1 through Visit 7) immunogenicity data will be included in the analyses for the Primary PP set and the Primary ITT set. Part B (Visit 12 through Visit 19) immunogenicity data will be included in the analyses for the Persistence PP set and the Persistence ITT set.

An exploratory analysis of serum neutralizing antibody titers will be performed using the PRNT80 assay (in addition to PRNT50 assay that used for secondary objectives).

11. Interim Analysis

Following completion of each dose level cohort in Part A, the database will be locked for that cohort and safety and/or immune testing results through 28 days following the final vaccination will be analyzed. As dose escalation occurs, cumulative analyses will be included for each subsequent data lock to allow for all prior dose level cohorts to be analyzed by dose level and in aggregate for VAL-181388 exposure. Also an interim analysis of safety, reactogenicity immunogenicity data collected from Day 1 to Month 7 will be conducted. Immunogenicity and safety data, including analyses of change from

baseline, where applicable, will be summarized for each dose level cohort and combined placebo group. These analyses will be performed by an unblinded team, independent of the study team. Access to individual listings will be restricted to identified Sponsor members and the clinical research organization unblinded team. Study sites will remain blinded. This analysis will provide information regarding short-term antibody persistence.

12. References

Centers for Disease Control and Prevention. Chikungunya virus geographic distribution [updated 22 Apr 2016; cited 2016 Sep 09]. Available from:
<http://www.cdc.gov/chikungunya/geo/index.html>.

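### The Primary Per-Protocol set is fixed once per subject, not per visit: a late Visit 7 draw removes a valid Visit 4 titer, and a one-dose titer may enter the Visit 7 summary

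*SAP*

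**What the plan says.** SAP 5.3.4 judges Primary PP membership over Part A as a whole. Apart from having no major violation, the subject must have "received vaccination within the acceptable vaccination window (their full dose(s) of assigned study drug), had blood collection within accepted visit windows", and must have "had both a pre-vaccination blood sample and at least 1 blood sample at Visit 4 or Visit 7 available for immunogenicity testing". One sentence works at the level of a time point: "In the case where there is not a paired sample for the specific time point that data will not be included in the analysis". It asks whether a pair exists. It does not ask how many doses preceded the sample.

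SAP Section 10 applies the set without distinction by visit: "Part A (Visit 1 through Visit 7) immunogenicity data will be included in the analyses for the Primary PP set and the Primary ITT set". Summaries are by treatment group and time point, not by number of doses received.

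Protocol 3.1 has the Visit 4 sample drawn before dose 2. Under Protocol 3.4.6, subjects who miss dose 2 through not keeping the visit schedule are asked for a "second immune test at 56 (+10) days (Visit 7) following the first vaccination". Protocol 3.3.1 keeps subjects who refuse further vaccination on all planned visits. SAP 5.3.5 defines the ITT sets as supportive and admits missed vaccinations and exceeded windows. The Persistence PP set is a subset of the Primary PP set.

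**The concern.** The two Part A post-vaccination samples answer different questions. Visit 4 shows the response to dose 1; Visit 7 shows the response after dose 2. A subject can be valid for one and not for the other, and a single subject-level flag cannot express that.

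This matters because SAP 5.3.4 ties the PP sets to the primary immunogenicity assessments, the secondary objective uses immunogenicity to inform the choice of dose, and Protocol 1.6 counts assessment after each of the two vaccinations among the purposes of the sampling plan. Two things could go wrong. One-dose titers could be averaged into a two-dose result. Or subjects could be removed from the post-dose-1 result for reasons that arose after that sample was taken. The second is a form of selection: Protocol 3.3.1 allows vaccination to be stopped after related adverse events of Grade 3 or higher, and Protocol 1.3 reports that adverse events with the sponsor's similar influenza vaccines appeared dose related. Such removals could therefore differ between dose groups.

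**Working it through.** **Planned numbers.** SAP 5.1: "Approximately 60 subjects (20 per cohort) are planned to be randomized, 15 receiving VAL-181388 and 5 receiving placebo within each cohort". From Protocol 3.1, sentinel plus expansion gives 3 + 12 = 15 active and 1 + 4 = 5 placebo, so 20 per cohort and 3 × 20 = 60. The plan's figure is reproduced. There is no power or precision figure to check.

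**What the text does, case by case**

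- *Both doses, valid Visit 4 sample, Visit 7 draw out of window.* The subject fails the blood-collection criterion for Part A and leaves the set, so the Visit 4 PP result goes too. This does not depend on how the dosing wording is read.
- *Dose 1 only, Day 56 (+10) sample given, one dose qualifies.* If the 56 (+10) window counts as accepted, the titer enters the Visit 7 PP GMT, GMR and seroresponse. SAP Table 13-1 shows only 28 (+7) days from the most recent vaccination. If that alone governs, the draw is out of window and the subject leaves the set, as in the first case.
- *Dose 1 only, both doses required.* The subject leaves the set and the Visit 4 PP result is lost.
- *Dose 1 only, no Visit 7 sample, one dose qualifies.* The pairing sentence keeps the subject at Visit 4 and omits them at Visit 7. This is correct handling.

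**Size of dilution at Visit 7.** Assumptions, because the documents give no human titers for this vaccine and no missed-dose rate: n = 15 in the dose group, k one-dose subjects, and two-dose titers R times one-dose titers. Then GMT(all) / GMT(two-dose only) = R^(−k/15).

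- R = 4: 4^(−1/15) = 0.912 and 4^(−2/15) = 0.831, so 9% and 17% lower.
- R = 10: 10^(−1/15) = 0.858 and 10^(−2/15) = 0.736, so 14% and 26% lower.
- Over R = 2 to 16 and k = 1 to 4, the ratio runs from 0.96 to 0.48.

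For seroresponse, take the extreme case with k = 2 in which every two-dose subject responds and neither one-dose subject does. The pooled result is 13/15 = 86.7% (Clopper-Pearson 95% CI 59.5 to 98.3), against 13/13 = 100% (75.3 to 100) among two-dose subjects.

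**Size of loss at Visit 4.** The log-scale CI half-width is proportional to t(0.975, n−1)/√n.

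- n = 15: 2.145/3.873 = 0.554.
- n = 13: 2.179/3.606 = 0.604.
- Ratio 0.604/0.554 = 1.09.

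With an assumed SD of 0.4 on log10 titer, the fold half-width goes from 1.67 to 1.74. If the two dropped subjects had titers S-fold below the rest, GMT(kept)/GMT(all) = S^(2/15), which is 1.10 for S = 2 and 1.20 for S = 4.

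**Counts for k = 2, Visit 4 / Visit 7.** One dose qualifies and both give an accepted Visit 7 sample: 15 / 15. Both doses required: 13 / 13. Per-visit eligibility: 15 / 13.

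**The case against.** The strongest reply is that requiring both doses is the natural reading. The assigned regimen is two injections, so a subject who misses dose 2 has not had the full assigned drug. The PP set is then an ordinary completer set, Visit 7 contains only two-dose subjects, and using the same people at both visits helps a within-subject comparison. The precision cost at Visit 4 is small. ITT keeps the Visit 4 values, and all data are listed. SAP Section 5 counts study day from the most recent vaccination, so a one-dose Day 56 draw would not carry the same study day as a two-dose Visit 7 draw. A separate document on major violations might also settle matters. Finally, "Formal sample size calculations were not performed as this is a descriptive safety and immunogenicity study with no formal null hypotheses being tested".

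Much of this stands. Under the two-dose reading the Visit 4 estimate is selected and slightly less precise, not miscalculated, and no one-dose titer reaches Visits 7, 12 or 19. A reader might infer that every one-dose subject is mishandled on either reading. The documents do not support that, since one with no Visit 7 sample is handled properly if one dose qualifies. Nor would such a subject be counted as a two-dose responder: they enter a mean and a denominator, may well not respond, and the likely effect is dilution.

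The reply leaves three things open. The wording does not say that both doses are required. The separate document is described as a process for determining major violations, whereas 5.3.4 lists dosing, window and sample criteria apart from these. And the loss of Visit 4 through a late Visit 7 draw follows on any reading of the dosing phrase.

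**Conclusion.** The point holds as a fault in how the set is built. One subject-level flag serves two visits with different validity conditions. It certainly removes some valid Visit 4 results from the PP analysis when Visit 7 is out of window. It may also admit one-dose titers at Visit 7, if one dose qualifies and the 56 (+10) window is accepted.

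The 9% to 26% dilution figures apply only under that second condition and rest on assumed titer gaps and assumed counts of one-dose subjects. Without it, the effect is a Visit 4 interval about 9% wider for two exclusions, plus possible selection whose size cannot be judged from the documents.

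A reader might infer that the problem passes into the persistence results regardless. Mixing of one-dose titers reaches Visits 12 and 19 only if one dose qualifies; under the two-dose reading the nested set is free of it.

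No alpha or power is affected. Importance lies between worth considering and should be done, because the trial is descriptive and no missed-dose rate is given, while the change is cheap.

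**What to change.** In SAP 5.3.4, define PP eligibility per visit:

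- **Visit 4:** dose 1 received in full as randomised; Visit 1 and Visit 4 samples in window; no major violation up to Visit 4.
- **Visit 7:** both doses received in full and in window; Visit 1 and Visit 7 samples in window; no major violation up to Visit 7.
- **Visits 12 and 19:** both doses received in full and in window; the sample for that visit in window; the existing pairing and major-violation conditions kept.

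State that these flags replace the single Part A flag in Section 10. A separate display of dose-1-only subjects in the ITT tables is optional.

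The cost is SAP wording and one population flag per visit in place of one per subject. No new data or visits are needed, and the SAP already refines the protocol's single PP set by splitting it into two. Denominators will differ slightly between visits. Where a like-for-like comparison of Visit 4 with Visit 7 is wanted, show it in subjects eligible at both.

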5.3.5. Intent-to-Treat Sets

The ITT sets will provide supportive analyses, and will be defined separately for Part A and the entire study to support the primary assessments of immunogenicity in Part A and immune persistence in Part B.

The Primary ITT set will include all subjects in the Randomized set who, in Part A (Visit 1 through Visit 7), had at least 1 post-vaccination blood sample at Visit 4 or Visit 7 available for immunogenicity testing regardless of protocol violations, exceeded visit windows, missed vaccination, or missing data.

The Persistence ITT set will include all subjects in the Primary ITT set who, in Part B (Visit 8 through Visit 19), had at least 1 blood sample at Visit 12 or Visit 19 available for immunogenicity testing regardless of protocol violations, exceeded visit windows, missed vaccination, or missing data.

All subjects in the ITT sets will be analyzed according to the study drug the subject was randomized to receive and not according to what was actually received, in the event there is a discrepancy.

6. Subject Disposition

6.1. Disposition

Subjects' disposition will be presented in a data listing.

The total number of subjects who receive each vaccination, who complete and discontinue the study, and who are included in each analysis set will be summarized. The number of subjects, who discontinue from the study, both overall and according to the reasons for discontinuation, will also be summarized. The reason for discontinuation can be:

- AE
- death
- lost to follow-up
- non-compliance with study drug
- physician decision
- pregnancy
- protocol deviation
- site terminated by sponsor
- study terminated by sponsor
- withdrawal by subject

- other

The summaries will be presented by treatment group as defined in Section 5.

6.2. Inclusion and Exclusion Criteria Deviations

Inclusion and exclusion criteria deviations will be presented in a listing.

6.3. Major Protocol Violations

Major protocol violations will be presented in a listing. These data will be provided as a .csv file from agreements made at the Protocol Deviation Meeting at a minimum prior to database lock. SAS listings will be provided to support this meeting, which is held after the completion of each dose level (or every six months) and just prior to database lock.

7. Demographics and Baseline Characteristics

7.1. Demographics

Demographic information will be listed and summarized. Descriptive statistics will be calculated for the following continuous demographic and baseline characteristics: age (years, calculated as the integer part of [date of informed consent - date of birth]/365.25), weight (kg), height (cm), and body mass index (BMI) (kg/m^2). Frequency counts will be tabulated for the categorical variables gender, race, and ethnicity. The summaries will be presented by treatment group as defined in Section 5 for subjects in the Safety set.

7.2. Medical History

Medical history data will be presented in a listing.

8. Treatments and Medications

8.1. Prior and Concomitant Medications

Information about prior medications (including any prescription or over-the-counter medications, vaccines, or blood products) taken by the subject within the 30 days before providing informed consent (or as designated in the inclusion/exclusion requirements) will be recorded in the subject's electronic case report form (eCRF).

In Part A of the study, concomitant medications include all medications (including vaccination outside of trial) taken by the subject from the time of signing the informed consent form (ICF) through 28 days after the second vaccination (Visit 7) and will be

recorded in the eCRF. In Part B, receipt of immunomodulators (including vaccines), immunosuppressants, or other concomitant medications that could potentially impact immune response will be collected through the end-of-study (EOS) visit.

Concomitant medications (including vaccinations) will be coded using the World Health Organization Drug (WHODrug) Dictionary. If prohibited drug therapy is taken, a joint decision will be made by the investigator and the Sponsor to continue or withhold further vaccination of the subject based on the time the medication was administered and its pharmacology and pharmacokinetics, and whether the use of the medication will compromise the subject safety or interpretation of the data. It is the investigator's responsibility to ensure that details regarding the concomitant medication are adequately recorded in the eCRF.

Prior and concomitant medication will be coded using the WHO Drug Dictionary and be listed. Concomitant medications taken within 28 days post each vaccination, and analgesic or antipyretic medications taken within 7 days post each vaccination will be summarized. The summaries will be presented by treatment group as defined in Section 5 for subjects in the Safety set.

8.2. Medical and Surgical Procedures

Medical or surgical procedures will be presented in a data listing.

8.3. Study Drug Administration

Study drug administration will be presented in a data listing.

9. Safety Analysis

Safety assessments will include monitoring and recording of solicited (local and systemic reactogenicity events) and unsolicited AEs; SAEs; AESIs; clinical laboratory test results including hematology, serum chemistry, coagulation, and urinalysis; vital sign measurements; and physical examination findings. The Toxicity Grading Scale for Healthy Adult and Adolescent Volunteers Enrolled in Preventative Vaccine Clinical Trials (CBER 2007) will be used to categorize solicited reactogenicity, safety laboratory test results, and vital sign measurements observed during this study.

